RUN DATE: DDMMYYYY hh:mm

CureVac AG
CV-7202-104

Statistical Analysis Plan
24 February 2022

Sponsor Clinical Study Report
Protocol number Page x of y
14.3.1.1.4.7 Day of First Onset of Systemic Solicited Adverse Events Post Dose 1, Safety Analysis Set

Programming note:

Repeat table 14.3.1.1.4.4 for systemic solicited adverse events, categories: Temperature, Headache, Fatigue, Chills, Myalgia, Arthralgia, Nausea/ Vomiting and Diarrhea.

CureVac AG
CV-7202-104

Statistical Analysis Plan
24 February 2022

Sponsor Clinical Study Report
Protocol number Page x of y
14.3.1.1.4.8 Day of First Onset of Systemic Solicited Adverse Events Post Dose 2, Safety Analysis Set

Programming note:

Repeat table 14.3.1.1.4.5 for systemic solicited adverse events, categories: Temperature, Headache, Fatigue, Chills, Myalgia, Arthralgia, Nausea/ Vomiting and Diarrhea.

CureVac AG
CV-7202-104

Statistical Analysis Plan
24 February 2022

Sponsor Clinical Study Report
Protocol number Page x of y
14.3.1.1.4.9 Day of First Onset of Systemic Solicited Adverse Events Post Dose 3, Safety Analysis Set

Programming note:

Repeat table 14.3.1.1.4.6 for systemic solicited adverse events, categories: Temperature, Headache, Fatigue, Chills, Myalgia, Arthralgia, Nausea/ Vomiting and Diarrhea.

CureVac AG
CV-7202-104

Statistical Analysis Plan
24 February 2022

Sponsor Clinical Study Report
Protocol number Page x of y
14.3.1.1.4.10 Day of First Onset of Related Systemic Solicited Adverse Events Post Dose 1, Safety Analysis Set

Programming note:

Repeat table 14.3.1.1.4.4 for related systemic solicited adverse events, categories: Temperature, Headache, Fatigue, Chills, Myalgia, Arthralgia, Nausea/ Vomiting and Diarrhea.

CureVac AG
CV-7202-104

Statistical Analysis Plan
24 February 2022

Sponsor Clinical Study Report
Protocol number Page x of y
14.3.1.1.4.11 Day of First Onset of Related Systemic Solicited Adverse Events Post Dose 2, Safety Analysis Set

Programming note:

Repeat table 14.3.1.1.4.5 for related systemic solicited adverse events, categories: Temperature, Headache, Fatigue, Chills, Myalgia, Arthralgia, Nausea/ Vomiting and Diarrhea.

CureVac AG
CV-7202-104

Statistical Analysis Plan
24 February 2022

Sponsor Clinical Study Report
Protocol number Page x of y
14.3.1.1.4.12 Day of First Onset of Related Systemic Solicited Adverse Events Post Dose 3, Safety Analysis Set

Programming note:

Repeat table 14.3.1.1.4.6 for related systemic solicited adverse events, categories: Temperature, Headache, Fatigue, Chills, Myalgia, Arthralgia, Nausea/ Vomiting and Diarrhea.

Sponsor

Clinical Study Report

Page x of y

Protocol number

14.3.1.2.1 Overall Summary of Unsolicited Adverse Events Within 28 Days After any Dose, Safety Analysis Set

Adverse Event Category [n (%) m]	CV7202 1 µg (N = xx)	CV7202 2 µg (N = xx)	CV7202 5 µg (N = xx)	Rabipur (N = xx)
All unsolicited adverse events	xx (xx.x%) xxx	xx (xx.x%) xxx	xx (xx.x%) xxx	xx (xx.x%) xxx
Related unsolicited adverse events	xx (xx.x%) xxx	xx (xx.x%) xxx	xx (xx.x%) xxx	xx (xx.x%) xxx
Serious adverse events	xx (xx.x%) xxx	xx (xx.x%) xxx	xx (xx.x%) xxx	xx (xx.x%) xxx
Related serious adverse events	xx (xx.x%) xxx	xx (xx.x%) xxx	xx (xx.x%) xxx	xx (xx.x%) xxx
Medically attended adverse events	xx (xx.x%) xxx	xx (xx.x%) xxx	xx (xx.x%) xxx	xx (xx.x%) xxx
Adverse events leading to withdrawal from study	xx (xx.x%) xxx	xx (xx.x%) xxx	xx (xx.x%) xxx	xx (xx.x%) xxx
Adverse events leading to discontinued vaccination	xx (xx.x%) xxx	xx (xx.x%) xxx	xx (xx.x%) xxx	xx (xx.x%) xxx
Adverse events of special interest	xx (xx.x%) xxx	xx (xx.x%) xxx	xx (xx.x%) xxx	xx (xx.x%) xxx

n = Number of subjects; m = Number of events; AEs on the day of vaccination and 28 subsequent days

Subjects reporting more than 1 event are counted only once for the subject count.

Percentages are based on total no. of subjects in each vaccination group.

Related: Adverse events which were assessed by the investigator as related to trial vaccine or study procedure.

PROGRAM SOURCE: tlf-###, DATA CUT OFF DATE: DDMMYYYY

RUN DATE: DDMMYYYY hh:mm

Programming note:

According to the SAP all unsolicited AE tables will be restricted to adverse events that occurred AFTER the first administration of the trial vaccine. If adverse events BEFORE are documented, these will be flagged and listed only.

Sponsor

Clinical Study Report

Page x of y

Protocol number

14.3.1.2.2 Overall Summary of Unsolicited Adverse Events Within 28 Days Post Dose 1, Safety Analysis Set

Adverse Event Category [n (%) m]	CV7202 1 µg (N = xx)	CV7202 2 µg (N = xx)	CV7202 5 µg (N = xx)	Rabipur (N = xx)
All unsolicited adverse events	xx (xx.x%) xxx	xx (xx.x%) xxx	xx (xx.x%) xxx	xx (xx.x%) xxx
Related unsolicited adverse events	xx (xx.x%) xxx	xx (xx.x%) xxx	xx (xx.x%) xxx	xx (xx.x%) xxx
Serious adverse events	xx (xx.x%) xxx	xx (xx.x%) xxx	xx (xx.x%) xxx	xx (xx.x%) xxx
Related serious adverse events	xx (xx.x%) xxx	xx (xx.x%) xxx	xx (xx.x%) xxx	xx (xx.x%) xxx
Medically attended adverse events	xx (xx.x%) xxx	xx (xx.x%) xxx	xx (xx.x%) xxx	xx (xx.x%) xxx
Adverse events leading to withdrawal from study	xx (xx.x%) xxx	xx (xx.x%) xxx	xx (xx.x%) xxx	xx (xx.x%) xxx
Adverse events leading to discontinued vaccination	xx (xx.x%) xxx	xx (xx.x%) xxx	xx (xx.x%) xxx	xx (xx.x%) xxx
Adverse events of special interest	xx (xx.x%) xxx	xx (xx.x%) xxx	xx (xx.x%) xxx	xx (xx.x%) xxx

n = Number of subjects; m = Number of events;

AEs on the day of vaccination and 28 subsequent days, but before dose 2 CV7202 or dose 3 of Rabipur.

Subjects reporting more than 1 event are counted only once for the subject count.

Percentages are based on total no. of subjects in each vaccination group.

Related: Adverse events which were assessed by the investigator as related to trial vaccine or study procedure.

PROGRAM SOURCE: tlf-###, DATA CUT OFF DATE: DDMMYYYY

RUN DATE: DDMMYYYY hh:mm

Programming note:

According to the SAP all unsolicited AE tables will be restricted to adverse events that occurred AFTER the first administration of the trial vaccine. If adverse events BEFORE are documented, these will be flagged and listed only. AEs on the day of vaccination and 28 subsequent days, but before dose 2 CV7202 or dose 3 of Rabipur.

Sponsor

Clinical Study Report

Page x of y

Protocol number

14.3.1.2.3 Overall Summary of Unsolicited Adverse Events Within 28 Days Post Dose 2 CV7202 or Dose 3 Rabipur, Safety Analysis Set

Adverse Event Category [n (%) m]	CV7202 2x1 µg (N = xx)	CV7202 2x2 µg (N = xx)	Rabipur (N = xx)
All unsolicited adverse events	xx (xx.x%) xxx	xx (xx.x%) xxx	xx (xx.x%) xxx
Related unsolicited adverse events	xx (xx.x%) xxx	xx (xx.x%) xxx	xx (xx.x%) xxx
Serious adverse events	xx (xx.x%) xxx	xx (xx.x%) xxx	xx (xx.x%) xxx
Related serious adverse events	xx (xx.x%) xxx	xx (xx.x%) xxx	xx (xx.x%) xxx
Medically attended adverse events	xx (xx.x%) xxx	xx (xx.x%) xxx	xx (xx.x%) xxx
Adverse events leading to withdrawal from study	xx (xx.x%) xxx	xx (xx.x%) xxx	xx (xx.x%) xxx
Adverse events leading to discontinued vaccination	xx (xx.x%) xxx	xx (xx.x%) xxx	xx (xx.x%) xxx
Adverse events of special interest	xx (xx.x%) xxx	xx (xx.x%) xxx	xx (xx.x%) xxx

n = Number of subjects; m = Number of events;

AEs on the day of vaccination and 28 subsequent days

Subjects reporting more than 1 event are counted only once for the subject count.

Percentages are based on total no. of subjects in each vaccination group.

Related: Adverse events which were assessed by the investigator as related to trial vaccine or study procedure.

PROGRAM SOURCE: tlf-###, DATA CUT OFF DATE: DDMMYYYY

RUN DATE: DDMMYYYY hh:mm

Programming note:

According to the SAP all unsolicited AE tables will be restricted to adverse events that occurred AFTER the first administration of the trial vaccine. If adverse events BEFORE are documented, these will be flagged and listed only.

Sponsor

Clinical Study Report

Page x of y

Protocol number

14.3.1.2.4 Summary of Unsolicited Adverse Events Within 28 Days by Maximum Intensity (Grade) After any Dose, Safety Analysis Set

Adverse Event Category [n (%)]	CV7202 1 µg (N = xx)	CV7202 2 µg (N = xx)	CV7202 5 µg (N = xx)	Rabipur (N = xx)
All unsolicited adverse events	Mild (grade 1) xx (xx.x%) Moderate (grade 2) xx (xx.x%) Severe (grade 3) xx (xx.x%)	xx (xx.x%) xx (xx.x%) xx (xx.x%)	xx (xx.x%) xx (xx.x%) xx (xx.x%)	xx (xx.x%) xx (xx.x%) xx (xx.x%)
Related unsolicited adverse events	Mild (grade 1) xx (xx.x%) Moderate (grade 2) xx (xx.x%) Severe (grade 3) xx (xx.x%)	xx (xx.x%) xx (xx.x%) xx (xx.x%)	xx (xx.x%) xx (xx.x%) xx (xx.x%)	xx (xx.x%) xx (xx.x%) xx (xx.x%)

n = Number of subjects; AEs on the day of vaccination and 28 subsequent days

Subjects reporting more than 1 event are counted only once for the subject count with highest intensity (grade).

Percentages are based on total no. of subjects in each vaccination group.

Related: Adverse events which were assessed by the investigator as related to trial vaccine or study procedure.

PROGRAM SOURCE: tlf-###, DATA CUT OFF DATE: DDMMYYYY

RUN DATE: DDMMYYYY hh:mm

Programming note:

According to the SAP all unsolicited AE tables will be restricted to adverse events that occurred AFTER the first administration of the trial vaccine. If adverse events BEFORE are documented, these will be flagged and listed only.

Sponsor
 Protocol number

 Clinical Study Report
 Page x of y

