10.3.5 Safety Analyses

The following safety and reactogenicity data will be summarized descriptively: vital signs, and vaccination site reactogenicity assessment.

The occurrence of solicited local and systemic AEs reported on the day of each vaccination and the 7 subsequent days and unsolicited AEs reported on the day of each vaccination and the 28 subsequent days will be presented.

The safety measurements will include:

1. AEs (type, intensity, frequency and relationship to vaccination), i.e. incidence and severity of AEs for both solicited local and systemic events (occurring on the day of vaccination and the 7 subsequent days) and unsolicited events (occurring on the day of vaccination and the 28 subsequent days).
2. SAEs, MAAEs and AEs leading to trial or vaccine withdrawal up to 12 months post last dose. After Visit 15 (Month 12), only SAEs and MAAEs that according to the

investigator are considered to be related to study vaccination will be collected.

3. Intercurrent medical conditions and AESIs throughout the trial.
4. Local reactogenicity assessment of injection site in all subjects.

Further, the incidence of AEs will be summarized in frequency tables by Medical Dictionary for Regulatory Activities (MedDRA) terms (system organ class [SOC] and preferred term [PT]). AEs that are reported as related to the test vaccine will be considered trial vaccine-related; missing classifications concerning trial vaccine relationship will also be considered trial vaccine-related.

Concomitant medications and vaccinations will be coded and summarized. Physical examination data will be listed.

Clinical laboratory test results with values below/above the reference range will be counted.

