- It is **not** acceptable for the investigator to send photocopies of the subject's medical records to [REDACTED] in lieu of completion of the AE/SAE CRF page.
- There may be instances when copies of medical records for certain cases are requested by [REDACTED]. In this case, all subject identifiers, with the exception of the subject number, will be redacted on the copies of the medical records before submission to [REDACTED].
- The investigator will attempt to establish a diagnosis of the event based on signs, symptoms, and/or other clinical information. Whenever possible, the diagnosis (not the individual signs/symptoms) will be documented as the AE/SAE.
- AESIs and cases of overdose must be documented and medically assessed by the investigator and the outcome described on the SAE/AESI/overdose report form.
- Pregnancy must be documented and medically assessed by the investigator and the outcome described on the Pregnancy Report Form which is to be sent to [REDACTED].

Assessment of Intensity

The investigator will make an assessment of intensity for each AE and SAE reported during the trial and assign it to 1 of the following categories [25]:

- Absent.**
- Mild:** An event that is easily tolerated by the subject, causing minimal discomfort and not interfering with everyday activities.
- Moderate:** An event that causes sufficient discomfort to interfere with normal everyday activities.
- Severe:** An event that prevents normal everyday activities. An AE that is assessed as severe should not be confused with a SAE. Severe is a category utilized for rating the intensity of an event; and both AEs and SAEs can be assessed as severe.

An event is defined as 'serious' when it meets at least one of the predefined outcomes as described in the definition of an SAE, not when it is rated as severe.

Assessment of Causality

- The investigator is obligated to assess the relationship between trial vaccine and each occurrence of each AE/SAE. Causality will be determined as:

- Related: There is a reasonable causal relationship between the IMP and the AE.
- Unrelated: There is no reasonable causal relationship between the IMP and the AE.
- A "reasonable possibility" of a relationship conveys that there are facts, evidence, and/or arguments to suggest a causal relationship, rather than a relationship cannot be ruled out.
- The investigator will use clinical judgment to determine the relationship.

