5. DETERMINATION OF SAMPLE SIZE

No statistically based sample size estimation was performed.

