6.4 Interim Analysis and Data Monitoring

One or more interim analyses (IAs) may be performed for this trial. The data will be cleaned for all subjects. The analyses will be based on a data snapshot. Analyses will be performed on the safety set or subsets of it based on the availability of data. No decision-making is planned for the IAs and no adjustments for the trial are planned based on the results.

It is not planned to discuss any difference between the IAs and the final analysis in the clinical trial report.

A first interim analysis was performed after 16 subjects had been vaccinated (10 subjects in the CV7202 5 µg group and 6 subjects in the Rabipur group) and observed until Visit 8. The first interim analysis focused on safety aspects only. It was planned in a standalone interim analysis plan, which was finalized on 6 February 2019.

The second interim analysis was performed after 53 subjects had been vaccinated (16 subjects in the CV7202 1 µg group, 16 subjects in the CV7202 2 µg group, 10 subjects in the CV7202 5 µg group and 11 subjects in the Rabipur group) and observed until Visit 12 (Day 57). The second interim analysis focused on safety and immunogenicity. The analysis was primarily based on the interim analysis plan as of 06 February 2019 and subsequent change requests for tables.

For details of data monitoring please refer to section 4.

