11.1 Safety Endpoints and Variables

The analysis of the primary objective to assess the safety and reactogenicity profile will examine solicited and unsolicited adverse events.

The primary endpoints include the following:

- The percentages of subjects with, and the frequencies and intensities of solicited local AEs reported on the day of vaccination and the 7 subsequent days (Days 1-8).
- The percentages of subjects with, and the frequencies, intensities, and relationship to vaccination of solicited systemic AEs reported on the day of vaccination and the 7 subsequent days (Days 1-8).
- The duration (in days) of solicited local AEs, of solicited systemic AEs, and of the individual solicited AEs.
- The percentages of subjects with and frequencies and intensities of any unsolicited and related unsolicited AEs reported on the day of vaccination and the 28 subsequent days (Days 1-29).

- The percentages of subjects with and frequencies and relationship to vaccination of any serious AEs (SAEs) and any medically attended AEs (MAAEs) up to 12 months after the last dose.
- The percentages of subjects with and frequencies and relationship to vaccination of any AEs of special interest (AESIs) up to 12 months after the last dose.

Secondary safety endpoints are:

- The percentages of subjects with and frequencies of SAEs and MAAEs related to study vaccination from 12 months after the last dose up to 24 months after the last dose (trial end).
- The percentages of subjects with and frequencies and relationship to vaccination of any AESIs from 12 months after the last dose up to 24 months after the last dose (trial end).

Further safety variables include the following:

- Extent of exposure
- Physical examination, weight, BMI
- 12-Lead electrocardiogram
- Vital signs
- Safety laboratory - hematology, biochemistry, coagulation
- Laboratory - Urine dipstick pregnancy test, serum pregnancy test (human chorionic gonadotropin)

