11.2.2 Unsolicited Adverse Events

Serious AEs, intercurrent medical conditions, AEs leading to trial or vaccine withdrawal, AEs of special interest (AESIs) and MAAEs will be collected by the investigator in the eCRF throughout the trial.

AEs with a suspected potential immune-mediated disease etiology will be considered AESIs. The investigator will assess if an AE is an AESI. A list of AESIs is provided in Appendix 10 of the protocol.

AEs that are reported as related to the test vaccine will be considered trial vaccine-related; missing classifications concerning trial vaccine relationship will also be considered trial vaccine-related.

Every unsolicited AE will be assigned to a vaccination dose (number) by consideration of the period of 28 days after vaccination administration. Unsolicited AEs can be assigned to either day 1 to 28 (dose 1 for any vaccination group), or day 29 to 57 (dose 2 for 2-dose regimens or dose 3 for the Rabipur group). For the Rabipur group, vaccination dose 2 is administered 8 days after vaccination dose 1, therefore no assignment of unsolicited AEs to vaccination dose 2 is done for the Rabipur group.

All AE summaries will be restricted to those AEs that occurred after the first administration of the trial product. Any other AE (ie, AE starting after trial entry and before the first vaccination) will be reflected only in the data listings. If it cannot be determined whether the AE occurred after the first administration of the trial product due to a partial onset date, then it will be counted as such. Verbatim terms in the eCRFs will be mapped to preferred terms (PTs) and system organ classes (SOCs) using the Medical Dictionary for Regulatory Activities (version 21.0 or higher).

The occurrence of unsolicited AEs reported on the day of vaccination and the 28 subsequent days will be presented. In addition selected AE summary tables will be repeated for unsolicited AEs occurring at any time after the first administration of the trial product.

Each AE summary will be displayed by vaccination group and dose regimen. Summaries by vaccination dose (number) will also be provided for all AEs. Summaries that are displayed by SOC and PT will be ordered by descending order of incidence of SOC and PT within each system organ class. Summaries will display number and percentage of subjects with at least 1 event and the number of events by vaccination group.

Summaries of the following types will be presented:

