12. CHANGES TO PROTOCOL-SPECIFIED ANALYSES

The protocol defines 2 PP sets as subsets of the FA set. Due to the small number of subjects per treatment group, it was decided that no per-protocol sets will be defined and used for analysis.

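### Six SAP table footnotes define a related adverse event more widely than the protocol and the SAP text, so a primary endpoint has two definitions

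*SAP*

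**What the plan says.** Three places give a vaccine-only rule. Protocol 10.3.5 states that "AEs that are reported as related to the test vaccine will be considered trial vaccine-related", and SAP 11.2.2 says the same. Both go on to say that "missing classifications concerning trial vaccine relationship will also be considered trial vaccine-related". In protocol Appendix 11, under the assessment of causality, the investigator chooses between two categories, and the positive one is "Related: There is a reasonable causal relationship between the IMP and the AE". There is no category for study procedures.

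The footnote in SAP Appendix D reads "Related: Adverse events which were assessed by the investigator as related to trial vaccine or study procedure". It stands, in the same words, under shells 14.3.1.2.1, 14.3.1.2.2, 14.3.1.2.3, 14.3.1.2.4, 14.3.1.3.1 and 14.3.1.3.2. The programming notes under those shells do not say how relatedness is derived.

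The endpoint at issue is primary in both documents (protocol 4.2, SAP 11.1): "The percentages of subjects with and frequencies and intensities of any unsolicited and related unsolicited AEs reported on the day of vaccination" and over the following 28 days. SAP section 12 lists one departure from the protocol, the per-protocol sets: "it was decided that no per-protocol sets will be defined and used for analysis".

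**The concern.** Going by the index in SAP Appendix C, these six shells are the only summaries with a row for related unsolicited events. The tables by system organ class and preferred term do not split by relationship. No summary therefore reports the endpoint under the protocol's own description, and a reader who wanted it would have to rebuild it from listing 16.2.7.1.1. Two programmers could each follow part of the SAP and deliver different numbers.

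Procedure-related events are plausible in a trial with this much venepuncture, and the procedures are not identical across groups: the 4-hour post-vaccination sample and the cytokine and transcriptome draws apply to CV7202 recipients only (protocol 9.5 and Table 9.3). The trial is descriptive, so these counts are themselves the result.

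**Working it through.** **No planned figure to reproduce.** SAP section 5 says "No statistically based sample size estimation was performed". The check compares the rules and then works out what one reclassified subject is worth.

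**1. The rules side by side.**

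| Place | Cause that makes an event related | Missing relationship |
|---|---|---|
| Protocol 10.3.5 | Vaccine | Counts as related |
| SAP 11.2.2 | Vaccine | Counts as related |
| Protocol Appendix 11 | IMP | Not addressed |
| Six shell footnotes | Vaccine or a study procedure | Not addressed |

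The firm conflict is in the second column. In the third column the footnotes are silent; they do not state an opposite rule.

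**2. What the rows feed.** Shells 14.3.1.2.1 to 14.3.1.2.4 report the primary endpoint for the 28-day window. Shells 14.3.1.3.1 and 14.3.1.3.2 cover the whole trial. The related-SAE row in the overall summaries (14.3.1.2.1 to 14.3.1.2.3 and 14.3.1.3.1) bears on the endpoint for the relationship of SAEs to vaccination.

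**3. What happens to the counts.** This depends on the eCRF, which SAP section 2 cites but which is not among the documents.

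- If it records procedure relatedness, the footnote rule adds procedure-only events. The number of events rises with each one. The number of subjects rises only when the subject has no vaccine-related event in that window.
- If it records relatedness to the vaccine only, the counts are the same under both rules and the footnote misdescribes them.

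**4. Size per subject.** One subject moves a group percentage by 100/n. Group sizes are in SAP 6.4 ("The second interim analysis was performed after 53 subjects had been vaccinated"): 16 + 16 + 10 + 11 = 53. The two-dose subgroups have 8 each (protocol 8.5).

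- 1 µg and 2 µg groups: 100/16 = 6.25 points
- Rabipur: 100/11 = 9.1 points
- 5 µg group: 100/10 = 10 points
- Two-dose subgroups: 100/8 = 12.5 points

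Columns with n=8 appear in shells 14.3.1.2.3 and 14.3.1.3.2.

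**5. Chance that any subject is affected.** The documents give no rate. Assume, for illustration, that each subject independently has probability q of being related under the footnote but not under the text. The chance of at least one such subject is 1 − (1 − q)^n.

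| Assumed q | n=16 | n=53 |
|---|---|---|
| 2% | 0.276 | 0.657 |
| 5% | 0.560 | 0.934 |
| 10% | 0.815 | 0.996 |

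This applies only if procedure relatedness is recorded.

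**6. Exposure to blood draws in the endpoint window.** From protocol Table 9.3, Days 1 to 29 cover Visits 3, 4, 5, 7 and 8: 120 + 25 + 94 + 33 + 60 = 332 ml at most, over 5 visits. After a second dose, Days 29 to 57 cover Visits 8 to 12: 60 + 25 + 94 + 24 + 38 = 241 ml at most, also over 5 visits.

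**The case against.** The strongest reply is that this is stray wording with no effect. Appendix 11 offers only related or unrelated to the IMP, and listing 16.2.7.1.1 shows a single relationship column. Both suggest that procedure relatedness may never have been collected. Nothing inferential rests on the row, and the listing shows the relationship event by event. That reply stands as far as the size is concerned: the documents do not show that any count changes. It does not remove the conflict, because the published table would still describe a primary endpoint in terms the protocol does not use.

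A reader might infer more than the documents support:

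- **That events with missing causality drop out.** The footnote does not exclude them, and SAP 11.2.2 still governs. Appendix 11 also requires a causality assessment for every event, so few should be missing.
- **That bruising or fainting at a blood draw would be reported as vaccine-related.** The footnote states its wider scope openly. The row would be a broader category than the protocol's, not a mislabelled one.
- **That the relevant exposure is 16 draw visits and about 809 ml.** Those totals span the whole trial, including pre-vaccination and long-term visits. The Days 1 to 29 window has 5 visits and at most 332 ml.

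**Conclusion.** Wrong as written. That two definitions of *related* exist for one primary endpoint follows from the text alone and needs no assumption. Section 12 does not declare the wider one.

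The effect on results is conditional. It is 6.25 to 12.5 percentage points per reclassified subject, depending on the group, and arises only if the eCRF captures relatedness to procedures. How many subjects that would involve is unknown. With no hypothesis test or sample-size calculation in the plan, the consequence is an ambiguous or misdescribed safety count, not a wrong test. This merits correction before the tables are produced, but it does not threaten the design.

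**What to change.** In all six shells, replace the footnote with one saying that related means related to the trial vaccine and that a missing relationship is counted as related. Derive the related rows, including the related-SAE row, by that rule. If the eCRF collects relatedness to procedures, show those events in a separate row.

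If the wider category is what the sponsor wants, or if the eCRF holds only one combined vaccine-or-procedure field so that a vaccine-only count cannot be derived, change SAP 11.2.2 to match and declare the change in section 12.

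The cost is six footnotes, one derivation line and a check of the annotated eCRF. No new data are needed.
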